## 9.0 Confidentiality, Privacy and Data Management

**For research being conducted at Penn State Hershey or by Penn State Hershey researchers only**, the research data security and integrity plan is submitted using "HRP-598 – Research Data Plan Review Form Application Supplement", which is available in the Library in CATS IRB (<http://irb.psu.edu>). Refer to Penn State College of Medicine IRB's "Standard Operating Procedure Addendum: Security and Integrity of Human Research Data", which is available on the IRB's website. **In order to avoid redundancy, for this section state "See the Research Data Plan Review Form" in section 9.0 if you are conducting Penn State Hershey research and move on to section 10.**

**For all other research**, in the sections below, describe the steps that will be taken to secure the data during storage, use and transmission.

### 9.1 Confidentiality

#### 9.1.1 Identifiers associated with data and/or specimens

List the identifiers that will be included or associated with the data and/or specimens in any way (e.g., names, addresses, telephone/fax numbers, email addresses, dates (date of birth, admission/discharge dates, etc.), medical record numbers, social security numbers, health plan beneficiary numbers, etc.).

If no identifiers will be included or associated with the data in any way, whether directly or indirectly, please indicate this instead.

The study data and/or specimens will not contain identifiable information. Names, addresses, telephone numbers, email addresses, date of birth, and visit dates will be linked to data and specimens via a code break list. Once enrolled in the study, all data collection will be performed under an assigned study ID# that is known only to the principal investigators, study coordinators and CRC staff (for purposes of blood collection and safety). These are the only persons able to connect the participant's identifiable information.

##### 9.1.1.1 Use of Codes, Master List

If identifiers will be associated with the data and/or specimens (as indicated in section 9.1.1 above), describe whether a master record or list containing a code (i.e., code number, pseudonyms) will be used to separate the data collected from identifiable information, where that master code list will be stored, who will have access to the master code list, and when it will be destroyed.

If identifiers are included or associated with the data as described in section 9.1.1 above, but no master record or list containing a code will be used, it will be assumed by the IRB that the investigator plans to directly link the identifiers with the data.

A master list containing a study ID number and participant's identity will be used. This will be stored on a central, password protected computer file or in locked study files located in locked research offices of the principal

investigators.

No data containing study ID#'s (code numbers) will be stored with the master list. Files will be maintained in locked file drawers or in password protected files to ensure security. Upon completion of data collection, only the investigators and study coordinator will have access to the list. This list will be destroyed 3 years after publication of the study results.

#### **9.1.2 Storage of Data and/or Specimens**

Describe where, how and for how long the data (hardcopy (paper) and/or electronic data) and/or specimens will be stored. NOTE: Data can include paper files, data on the internet or websites, computer files, audio/video files, photographs, etc. and should be considered in the responses. Refer to the "Investigator Manual (HRP-103)" for information about how long research records must be stored following the completion of the research prior to completing this section. HRP-103 can be accessed by clicking the Library link in CATS IRB (<http://irb.psu.edu>).

Please review [Penn State's Data Categorization Project](#) for detailed information regarding the appropriate and allowable storage of research data collected according to [Penn State Policy AD71](#). Although the IRB can impose greater confidentiality/security requirements (particularly for sensitive data), the IRB cannot approve storage of research data in any way or using any service that is not permissible by [Penn State Policy AD71](#).

Data will be stored in password protected computer files, locked file cabinets, locked offices, and using an identification coding system. Data will be stored for 3 years after the research has been published.

Consent forms will be stored in a locked office in a locked filing cabinet. Consent forms will be stored for at least 3 years after the completion of the research.

#### **9.1.3 Access to Data and/or Specimens**

Identify who will have access to the data and/or specimens. This information should not conflict with information provided in section 9.1.1.1 regarding who has access to identifiable information, if applicable.

The principal investigators, co-investigator, study coordinators and trained study personnel will have access to data and specimens.

#### **9.1.4 Transferring Data and/or Specimens**

If the data and/or specimens will be transferred to and/or from outside collaborators, identify the collaborator to whom the data and/or specimens will be transferred and how the data and/or specimens will be transferred. This information should not conflict with information provided in section 9.1.1.1 regarding who has access to identifiable information, if applicable.

After collection, serum and plasma are transferred to ~1 mL aliquots – these vials contain only the participants study ID #, sample type (serum or plasma) and time point. The vials are then boxed and stored in a locked -80 degree freezer until all data collection is complete. Fecal samples will also be stored in a locked -80 degree freezer and the vials will contain no identifying information. Once the study is complete the samples will be sorted and

shipped on dry ice via FedEx or a Quest Courier to the following sites for analysis: (No identifying information is provided with the samples)

Serum/Plasma:

- Quest diagnostics, [name]

Fecal samples:

- Wright Labs LLC, [name]

## 9.2 Subject Privacy

This section must address subject privacy and NOT data confidentiality.

Indicate how the research team is permitted to access any sources of information about the subjects.

Describe the steps that will be taken to protect subjects' privacy interests. "Privacy interest" refers to a person's desire to place limits on whom they interact with or to whom they provide personal information.

Describe what steps you will take to make the subjects feel at ease with the research situation in terms of the questions being asked and the procedures being performed. "At ease" does not refer to physical discomfort, but the sense of intrusiveness a subject might experience in response to questions, examinations, and procedures.

Once enrolled in the study, all data collection will be performed under an assigned study ID# that is known only to the principal investigators, co-investigators, study coordinators and CRC staff (for purposes of blood collection and safety). These are the only persons able to connect the participant's identifiable information. In addition, all study personnel have conducted IRB training and are aware of the importance involved with maintaining privacy and confidentiality when interacting with participants in any setting.

All clinical visits are conducted at the CRC by highly trained clinical staff. The CRC maintains the same level of privacy and sterility that is expected in a hospital setting and all clinical assessments are conducted within private rooms.

## 10.0 Data and Safety Monitoring Plan

**This section is required when research involves more than Minimal Risk to subjects.** As defined in "SOP: Definitions (HRP-001)", available in the Library in CATS IRB (<http://irb.psu.edu>), Minimal Risk is defined as the probability and magnitude of harm or discomfort anticipated in the research that are not greater in and of themselves than those ordinarily encountered in daily life or during the performance of routine physical or psychological examinations or tests. For research involving prisoners, Minimal Risk is the probability and magnitude of physical or psychological harm that is normally encountered in the daily lives, or in the routine medical, dental, or psychological examination of healthy persons. **Please complete the sections below if the research involves more than minimal risk to subjects OR indicate as not applicable.**

### 10.1 Periodic evaluation of data

Describe the plan to periodically evaluate the data collected regarding both harms and benefits to determine whether subjects remain safe.

Not applicable

**10.2 Data that are reviewed**

Describe the data that are reviewed, including safety data, untoward events, and efficacy data.

Not applicable

**10.3 Method of collection of safety information**

Describe the method by which the safety information will be collected (e.g., with case report forms, at study visits, by telephone calls and with subjects).

Not applicable

**10.4 Frequency of data collection**

Describe the frequency of data collection, including when safety data collection starts.

Not applicable

**10.5 Individuals reviewing the data**

Identify the individuals who will review the data. The plan might include establishing a data and safety monitoring committee and a plan for reporting data monitoring committee findings to the IRB and the sponsor.

Not applicable

**10.6 Frequency of review of cumulative data**

Describe the frequency or periodicity of review of cumulative data.

Not applicable

**10.7 Statistical tests**

Describe the statistical tests for analyzing the safety data to determine whether harms are occurring.

Not applicable

**10.8 Suspension of research**

Describe any conditions that trigger an immediate suspension of research.

Not applicable

**11.0 Risks**

List the reasonably foreseeable risks, discomforts, hazards, or inconveniences to the subjects related to the subjects' participation in the research. For each potential risk, describe the probability, magnitude, duration, and reversibility. Consider all types of risk including physical, psychological, social, legal, and economic risks. If applicable, indicate which procedures may have risks to the subjects that are currently unforeseeable. If applicable, indicate which procedures may have risks to an embryo or fetus should the subject be or become pregnant. If applicable, describe risks to others who are not subjects.

Please keep in mind that loss of confidentiality is a potential risk when conducting human subject research and should be addressed as such.

Gastrointestinal symptoms:

Some participants may experience GI (stomach) upset from the changes to their diet with incorporation of the test foods; symptoms may include, but are not limited to, any of the following: constipation/diarrhea, nausea, and bloating. This will likely subside once the participant becomes accustomed to the study foods.

**Food Allergies:**

Individuals will be asked to report any food allergies during the telephone screen, however it is possible that an unknown food allergy may manifest during the study. This is most likely to occur within the first week of the treatment period. Each day participants will be asked to complete a daily monitoring form so that we may track any adverse events, including potential food allergies, and identify the source as soon as possible. In addition, we ask participants to please inform study staff immediately should any adverse events occur.

**Blood Sampling:**

Blood draws often cause mild pain, swelling or bleeding. There may be some bruising (blood under the surface of the skin), which can be minimized by pressing on the site after the needle is removed. There is also a slight chance of infection, dizziness or fainting. These risks will be minimized and most likely eliminated by having trained staff draw the blood in a clinical setting using sterile supplies. If dizziness or fainting occurs, the symptoms will be alleviated by having the participant lie flat with their feet raised. If these should occur, the participant may be asked to remain at the clinic until the nurses have checked the participant's blood pressure and are sure the participant is ok to leave.

**SphygmoCor (Pulse Wave Analysis and Pulse Wave Velocity):**

There are no known risks associated with these measurements. The sensation of pressure from the blood pressure cuff or hand-held probe may be uncomfortable. There is a possibility for red blotching or mild bruising (petechiae) appearing on the skin above and below the location of the blood pressure cuff. Studies indicate that petechiae are rare (occurring in less than ½ of 1% of patients) and it is typically not uncomfortable and does not require treatment.

**Loss of Confidentiality:**

There is always a potential for loss of confidentiality despite our best efforts. To prevent this from occurring all records are coded with a unique ID number and no names are used. Records containing names or other identifying information are kept under lock at the PI's research office. All records associated with an individual's participation in the study will be subject to the usual confidentiality standards applicable to medical records. In the event of publication of this research, no personal identifying information will be disclosed.

**Fecal Sample Collection:**

Some participants may experience a certain level of embarrassment or discomfort from being asked to collect stool samples.

## **12.0 Potential Benefits to Subjects and Others**

### **12.1 Potential Benefits to Subjects**

Describe the potential benefits that individual subjects may experience from taking part in the research. If there is no direct benefit to subjects, indicate as such. Compensation is not considered a benefit. Compensation should be addressed in section 14.0.

Participants will receive their screening laboratory results, including a complete blood count, interpretation of liver and kidney function, and blood lipid values, at no cost.

## 12.2 Potential Benefits to Others

Include benefits to society or others.

The findings of this study will be applicable to the 84 million adults living with pre-diabetes in the US, and if shown to improve glycemic control the results may be extrapolated to the 30 million adults living with diabetes in the U.S.. This equates to approximately one third of the U.S. population, which demonstrates the substantial public health burden attributable to pre-diabetes and diabetes. Further demonstrating the critical need for strategies to improve glycemic control is data showing that 46% of adults with diabetes have suboptimal glycemic control. This novel study will empirically test the hypothesis that nighttime peanut consumption improves fasting glucose levels, and thus if supported this non-pharmaceutical treatment strategy is likely to have substantial clinical and public health implications. The findings of this research will be published in peer reviewed journals and these papers will likely be cited by clinical management guidelines and inform dietary recommendations. Therefore, the findings of this research are likely to inform clinical practice and dietary guidelines for individuals with impaired fasting glucose.

## 13.0 Sharing Results with Subjects

Describe whether results (study results or individual subject results, such as results of investigational diagnostic tests, genetic tests, or incidental findings) will be shared with subjects or others (e.g., the subject's primary care physicians) and if so, describe how it will be shared.

Screening results are provided to all potential participants (regardless of their eligibility status) within 2 weeks of their screening appointment. All screening results are reviewed by the Nurse Practitioner or Physician at the Clinical Center. Should any abnormal lab values be identified that warrant further evaluation the individual will be contacted (by the Study Coordinator) and asked to schedule a visit with their primary care physician. Individual results following each treatment period may be provided to participants upon request following completion of all study related data collection and analyses.

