### 3.2 Exclusion Criteria

List the criteria that define who will be excluded in your study.

We will not recruit participants who have chronic disease risk factors that are diagnostic of diabetes (fasting glucose  $> 126$  mg/dL) or hypertension (SBP  $> 160$  mm Hg or DBP  $> 100$  mm Hg). In addition, they will not be taking anti-hypertensive, lipid lowering or glucose lowering drugs. Individuals with established CVD, stroke, diabetes, liver, kidney, autoimmune diseases or inflammatory conditions such as gastrointestinal disorders or rheumatoid arthritis will not be eligible. Other exclusion criteria will include: use of supplements (psyllium, fish oil, soy lecithin, and phytoestrogens) and botanicals and not willing to cease for the duration of the study; women who are pregnant, lactating, planning to become pregnant or have given birth in the past year; weight loss of  $\geq 10\%$  of body weight within the 6 months prior to enrolling in the study; or smoking or use of any tobacco products in past 6 months. Participants with an allergy/intolerance/sensitivity to test foods will be excluded (i.e. peanuts, gluten, grain products, cheese). Individuals consuming  $> 14$  alcoholic drinks/week or not willing to avoid alcohol consumption for 48 hour prior to test visit will be ineligible for the study.

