### 7.2.1 EXAMPLE: Visit 1 or Day 1 or Pre-test, etc. (format accordingly)

Provide a description as defined above and format accordingly.

Screening: The clinical visit will consist of filling out forms (informed consent, medical history, personal information); measuring height and weight so that BMI can be calculated; and measuring blood pressure to determine eligibility. If blood pressure is >140/90 mmHg at screening the individual will require written approval from their Primary Care Physician prior to enrolling the study. Women of child bearing potential will provide a urine sample for a pregnancy test. If after these measurements, it is determined that the subject is still eligible, a blood sample will be taken and a complete blood count, including liver and kidney function and a blood lipid panel will be performed (approximately 19 mls of blood or ~1.25 tablespoon will be taken). If the initial blood draw is unsuccessful it may need to be repeated, with permission from the participant. In addition, if a potential participant takes thyroid medicine they must provide a current (within 6 months) lab test. If they do not have one, an extra 3.5 ml (0.2 Tbsp) of blood will be taken to conduct a thyroid test. If all eligibility criteria are met, participants will be scheduled for their baseline measurements. Baseline visits typically occur within 1-2 weeks following the screening appointment.

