### 7.2.2 EXAMPLE: Visit 2 or Day 2 or Post-test, etc. (format accordingly)

Provide a description as defined above and format accordingly.

Baseline and endpoint visits (8 total):

At the beginning and end of each diet period, two fasting blood samples will be collected (separated by at least 24 hours) for analysis of biochemical endpoints. Body weight will be taken

and vascular health assessments using the SphygmoCor will be performed at the beginning and end of each diet period. Participants will also complete a fecal collection at the beginning and end of each treatment period. Participants will complete a 24-hour dietary recall at the beginning and end of each treatment period.

**Plasma/serum analysis:** In addition to the blood taken at screening, 12 hour fasting blood samples also will be taken on two consecutive days at the beginning and end of each treatment period for a total of 8 times. Approximately 60 ml (about 4 Tbsp) will be collected across the two visits (30 ml per day). A typical American Red Cross blood donation is 1 pint (500 ml). Blood may be analyzed for the following: blood lipids and lipoproteins, glucose and insulin, and Fructosamine.

**Central Blood Pressure and Augmentation Index:** Following a 5-minute rest period, brachial artery systolic and diastolic blood pressure will be measured in the left arm using an automated blood pressure cuff. The cuff will reinflate and obtain a pulse wave form. Central blood pressure and wave reflection characteristics (augmentation index) will then be derived from the pressure waveforms using a validated transfer function with a SphygmoCor System (AtCor Medical, Sydney, Australia). This test will be performed in triplicate.

**Pulse Wave Velocity:** Arterial stiffness will be assessed by calculating the pulse wave velocity (PWV) between the carotid and femoral arteries while in the supine position. A cuff will be placed on the participant's thigh. The cuff will inflate during the test to record the pulse waveform in the femoral artery. A simultaneous measurement of the carotid artery pressure waveform will be obtained by an applanation tonometry sensor manually held in place above the carotid artery. PWV will subsequently be calculated by dividing the linear distance between the carotid and femoral sites by the transit time using the SphygmoCor system (AtCor Medical, Sydney Australia). This measurement will be performed in triplicate.

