### 7.3 Duration of Participation

Describe the duration of an individual subject's participation in the study.

Each participant will be involved in the study for approximately 16 weeks; two treatment periods each lasting 6 weeks, separated by a  $\geq$  4 week break. Participants will be expected to pick up the test foods

biweekly at the diet center on campus. At the beginning and end of each diet period, data collection (described above) will occur.

Total time for study visits, after the initial screening is approximately 6 hours. Times may vary and females will require an additional 5 minutes for a urine pregnancy test a baseline and the end of each diet period. The following is an estimate of the amount of time participants will spend in study activities:

- Screening appointment:  
Day 1: Forms, blood pressure, weight, height, blood draw – 45-60 minutes  
(pregnancy testing: females only – 5 minutes)
- Beginning of treatment period 1 and 2  
Day 1: blood draw, weight, PWA, PWV – 60 minutes  
(pregnancy testing: females only – 5 minutes)  
Day 2: blood draw – 30 minutes
- End of treatment period 1 and 2:  
Day 1: blood draw, weight, PWA, PWV – 60 minutes  
(pregnancy testing: females only – 5 minutes)  
Day 2: blood draw – 30 minutes
- Picking up food, fecal collections, and completing 24-hour diet recalls : ~ 5 hours

Total time for clinic and diet center visits from the beginning to the end of the study ~11 hours

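### Section 13 specifies review and referral of abnormal results at screening only; in-study glucose is assayed after data collection ends and returned only on request

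*Combined protocol and SAP*

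**What the plan says.** **Screening results.** Section 13.0 returns these to everyone screened, eligible or not, within 2 weeks. It names a reviewer, "All screening results are reviewed by the Nurse Practitioner or Physician at the Clinical Center", and an action, "Should any abnormal lab values be identified that warrant further evaluation the individual will be contacted". The study coordinator makes that contact and asks the person to see their primary care physician.

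**In-study results.** The same section then says: "Individual results following each treatment period may be provided to participants upon request following completion of all study related data collection and analyses".

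**When in-study results exist.** Section 9.1.4 says of the serum and plasma: "The vials are then boxed and stored in a locked -80 degree freezer until all data collection is complete". Shipment to the outside laboratory follows. Section 7.2.2 lists the analytes: "Blood may be analyzed for the following: blood lipids and lipoproteins, glucose and insulin, and Fructosamine". Although that sentence is permissive, section 1.2 makes fasting plasma glucose the primary endpoint, so these values will be produced.

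**The protocol's own limit.** Section 3.1 admits people with fasting glucose of at least 100 mg/dL. Section 3.2 excludes those with "chronic disease risk factors that are diagnostic of diabetes", given as above 126 mg/dL, and those on glucose-lowering drugs. No section refers to the limit after enrolment. The removal criteria in section 3.3.1 are non-compliance and withdrawn consent. Sections 10.1 to 10.8 are marked not applicable.

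**The concern.** The trial enrols people just below a limit that it describes as diagnostic, measures the same quantity again as its primary endpoint, and assigns nobody to look at individual values for the participant's sake. A person who fails screening is sure to receive a reviewed result. A person who is randomised and later gives a higher value learns of it only by asking, after the analyses are finished, and even then release is optional.

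What is at stake is participant protection. The study team would hold a fasting glucose above its own diabetes limit, in someone untreated at entry, with no planned step that brings it to that person's attention. The primary comparison of the two snacks is not affected.

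**Working it through.** The plan states no figure to reproduce here. The check sets the provisions side by side, with simple arithmetic for the number of samples and the delay.

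**1. Handling of a laboratory value, by stage**

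| | Screening (13.0) | In-study (9.1.4 and 13.0) |
|---|---|---|
| When assayed | In time for return within 2 weeks | After all data collection |
| Named reviewer | Nurse practitioner or physician | None stated |
| Contact if abnormal | Yes, by the study coordinator | None stated |
| Referral | Primary care physician | None stated |
| Return to participant | Everyone | Optional, on request, after analyses |

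For in-study results this is more than silence. Section 13.0 states a positive rule, return on request, and that rule leaves out anyone who does not ask.

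**2. Samples covered**

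Inputs are from section 7.2.2: two draws at each of the start and end of two periods.

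- Per participant: 2 × 2 × 2 = 8 fasting samples, at 4 time points.
- For the 45 planned completers (section 8.1): 45 × 8 = 360 samples with no written individual review.

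**3. Shortest delay**

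Inputs are from sections 7.1 and 7.3: 6 weeks of treatment, at least 4 weeks of wash-out, 6 weeks of treatment.

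- From first baseline draw to the same participant's last visit: 6 + 4 + 6 = 16 weeks at minimum.
- Section 9.1.4 holds vials until all data collection is complete, so anyone enrolled before the last participant waits longer. The documents give no accrual period, so no upper figure follows.
- For a participant who never asks, the plan provides no return at all.

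**4. Do other safeguards cover the assayed glucose?**

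- Daily monitoring forms (7.2.2) and their use to track adverse events (11.0) are self-reports. They do not contain glucose.
- A clinician attends clinical testing (16.4) but cannot see a value that has not been assayed.
- IRB reporting (19.1) covers harms judged unexpected and probably related to the research. It is not notice to the participant.

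These safeguards are real, but none acts on the assayed glucose.

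**5. How many participants?**

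This cannot be derived. It would need the distribution of usual glucose levels in the enrolled cohort and the within-person SD. Section 8.2 gives an SD of 23.4 mg/dL for sample size without saying whether it is within-person, between-person or of a difference. I give no frequency.

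**The case against.** The strongest defence is that this is a minimal-risk food study. Its template requires section 10 only above minimal risk, batch assay of stored samples is an open design choice, and participants already know from screening that their fasting glucose is raised. Anyone who wants their results can ask. The sentence about abnormal laboratory values is not itself confined to screening, although its place among the screening sentences points that way. Much of this stands. It supports batching and the absence of a monitoring committee. It does not explain why a value the team holds should reach only those who ask.

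A reader might infer more than the documents support:

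- **That safety review ends at screening.** It does not. Daily forms, adverse event tracking, a clinician at testing and IRB reporting all continue. What is confined to screening is the written review and referral of results.
- **That the sections contradict each other.** They do not give two instructions for the same value. Screening and in-study results are handled differently, and the difference is left unreconciled.
- **That participants are not told about blood pressure or pregnancy.** Section 7.2.1 says "If blood pressure is >140/90 mmHg at screening the individual will require written approval from their Primary Care Physician", and section 7.3 says "females will require an additional 5 minutes for a urine pregnancy test a baseline and the end of each diet period". Both measurements are made at visits, so freezing does not apply to them. The plan states no handling step for in-study findings, but that is missing detail and not evidence that a finding is withheld.

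**Conclusion.** The concern holds for in-study laboratory results, and for glucose in particular. Review, contact and referral are specified for screening results only. In-study samples are assayed after data collection ends, and individual results are released at the team's option, on request. A participant above the protocol's own diabetes limit need never be told. The gap covers 8 samples per participant, with at least 16 weeks before the first can be assayed and no return for those who do not ask.

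This merits a change on participant-protection grounds but does not threaten the primary analysis. It should not be read as showing that harm will occur or that many participants will cross the limit. A single value above 126 mg/dL may reflect ordinary within-person variation, which is why a clinician's judgement belongs in the process.

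The conclusion assumes that the consent form, which was not available for review, adds no return-of-results provision. If it does, section 13.0 still needs to agree with it.

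**What to change.** Reconcile sections 3.2, 9.1.4 and 13.0 by extending the review-and-contact process already in section 13.0 to in-study laboratory results:

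1. State that in-study results are reviewed by the nurse practitioner or physician when the laboratory reports.
2. State that the study coordinator sends results the reviewer judges to need further evaluation, without waiting for a request or for the statistical analyses. Other results can stay available on request.
3. Leave the choice of values and of any clinical action to the investigators, and record it in section 13.0.
4. Add a sentence saying how in-study blood pressure and pregnancy test findings are handled, since none is stated.

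The cost is one paragraph, matching consent wording, and clinician and coordinator time for flagged results. No extra blood or visit is needed. Section 9.1.1.1 keeps the master list, with coordinator access, until 3 years after publication, so participants can still be identified.

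The batched endpoint assay is unchanged. Because laboratory results are reviewed only after all data collection, that review cannot influence behaviour or treatment during the crossover. For the same reason it does not shorten the wait of 16 weeks or more for the assay. The gain is that participants who do not ask are still told.
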